**Slow Accrual Plan:**

The study will be monitored for accrual starting quarter 6. If study accrual is  $\leq 50\%$  on the MG arm at the end of quarter 6 (9 patients) or every 2 quarters afterwards, we will add additional study centers by offering this study to a larger NCTN consortium such as Alliance or NRG Oncology in order increase accrual.

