### 3.0 PATIENT ELIGIBILITY CRITERIA

#### 3.1 Patient Sample

Sample Size:

Minimum: 28 patients / Maximum: 62 patients

Accrual Rate:

1 patient per month

Gender:

Male and female

Age:

Patients must be at least 18 years of age.

Race:

Minorities will be actively recruited. No exclusion to this study will be based on race or ethnicity.

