### **4.0 TREATMENT PLAN**

This is a Phase II, open-label, multicenter efficacy study of encorafenib in combination with binimetinib in adult patients with recurrent BRAF-V600E/K mutated high-grade primary brain tumors. The goal of this study is to estimate the efficacy of encorafenib and binimetinib as measured by radiographic response in recurrent high-grade primary brain tumors.

[figure not shown]
There are two arms: medical and surgical. All subjects on the medical arm must have histologically confirmed high-grade glioma (including but not limited to glioblastoma (GBM), anaplastic astrocytoma (AA), and gliosarcoma), anaplastic pleomorphic xanthoastrocytoma (aPXA) or other high-grade primary brain tumor (including but not limited to anaplastic ganglioglioma (AG), and anaplastic ependymoma) that is recurrent after first-line treatment. Subjects on the surgical arm must have a high-grade glioma or a known BRAF-mutated low-grade glioma with high clinical suspicion for progression to high-grade.

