### **11.2 Sample Size Justification**

Sample size consideration for cohort 1 malignant gliomas (MG) and cohort 2 anaplastic PXAs:

Based on the information from prior clinical trials (Scientific rationale), the investigators consider the primary cohorts 1 (patients with AA or GBM) and 2 (Anaplastic PXAs) to share a similar null hypothesis of tumor response rate at 10% to be considered not clinically meaningful treatment effect and an alternative of 30% tumor response rate to be clinically desired treatment effect. A total of 23 patients is required per individual primary cohort 1 and cohort 2.

Cohort sample size estimation was based on a 2-stage design (minimax) with a futility analysis at end of first stage. Fourteen patients will be enrolled onto first stage. If no more than 1 response (7%) was observed among the initial 14 patients in a cohort, the cohort

would be terminated early and declared negative. Otherwise, nine more patients will be enrolled. If at least 5 responses (at least 22%) were observed among the 23 evaluable patients, the regimen would be considered worthy of further testing in this disease and the patient population. This design yields at least 85% power to detect a true response rate of at least 30% at a false positive rate of 10%. It yields at least 0.9 probability of a negative result if the true response rate is no more than 10%, with at least 0.58 probability of early negative stopping. The 2 primary cohorts will be evaluated independently.

The maximum total sample size for the two primary cohorts is 46 patients (23+23).

The sample size for the cohort 3 is 6 to 10 patients (other types of high-grade brain tumor that are not included in the primary cohort 1 or 2). This sample size is not based on statistical rationale but due to clinical feasibility. Patient enrollment will be considered completed at the time of completion of the enrollment in the cohort 1 and the cohort 2.

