In the correlative studies, there is a surgical cohort of 6 patients who are clinically surgical indicated for tissue PK study after initial treatment prior to surgery. There is no clinical or trial decision will be made based on outcome of the surgical cohort. Currently, prior information on amount of drug concentration in tumor tissue are lacking, especially with this combination treatment. However, 6 patients will have 90% power to detect an 80% true probability of BBB penetration, with .93 likelihood of rejecting a 30% true probability of BBB penetration.

Data analysis will be performed for each cohort independently. Tumor response rate will be estimated as proportion of number of tumor responders over number of patients in a cohort, as a binomial distribution (exact method) with 80% and 90% confidence intervals.

**Accrual Rate:** The expected accrual rate is one patient per month among 11 ABTC institutions.

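### Does the slow-accrual figure of 9 patients, written against the MG arm, need correcting?

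*Combined protocol and SAP*

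**What the plan says.** Section 11.2 gives one accrual rate: "The expected accrual rate is one patient per month among 11 ABTC institutions". Section 3.1 repeats it as "1 patient per month", in the same list as the whole-study size, "Minimum: 28 patients / Maximum: 62 patients".

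Under Slow Accrual Plan, "The study will be monitored for accrual starting quarter 6". The condition is accrual of 50% or less "on the MG arm at the end of quarter 6 (9 patients) or every 2 quarters afterwards". If it is met, the study is offered to a larger cooperative group so that centers can be added. Nothing else depends on it.

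MG is the label that Section 11.2 gives to cohort 1, which is planned at 23 patients. Cohort 2 (anaplastic PXA) is also planned at 23. For the others, "The sample size for the cohort 3 is 6 to 10 patients" and "there is a surgical cohort of 6 patients who are clinically surgical indicated". Section 4.0 uses the word arm differently: "There are two arms: medical and surgical". No accrual rate or share of accrual is given for MG.

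**The concern.** The figure of 9 follows exactly from the whole-study rate, yet the sentence applies it to one of four cohorts. Two people monitoring accrual could use different triggers: 9 or fewer MG patients, or half of an expected 9, meaning 4 or fewer. With 5 to 9 MG patients at quarter 6, one would open the study to another consortium and the other would not.

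If the trigger is 9 or fewer MG patients, and MG patients arrive in proportion to the planned cohort sizes, then 9 is at or above the expected count, not half of it. The rule would then fire more often than not in a study running exactly to plan. BRAF V600 mutations are rare in glioblastoma (1 to 5%, Section 2.1), so slow accrual is a real risk, and its one safeguard ought to be clear.

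**Working it through.** **Inputs.** Rate of 1 patient per month (Sections 3.1 and 11.2). First check at the end of quarter 6, which is 6 × 3 = 18 months. Cohort sizes 23, 23, 6 to 10, and 6 (Section 11.2), with maximum 23 + 23 + 10 + 6 = 62. The MG share of accrual is not stated, so it is an assumption and is varied below.

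**The plan's figure.** 1 × 18 = 18 patients expected in the whole study, and 0.50 × 18 = 9. This reproduces the 9 in the text.

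**Reading A: the trigger is 9 or fewer MG patients.** Treat the MG count at month 18 as Poisson with mean 18 × share. The probability of firing with the study on plan is P(X ≤ 9):

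| MG share of accrual | Mean at month 18 | P(X ≤ 9) |
|---|---|---|
| 23/62 | 6.68 | 0.862 |
| 23/52 (no cohort 3) | 7.96 | 0.721 |
| 29/62 (surgical patients counted as MG) | 8.42 | 0.663 |
| 23/46 (primary cohorts only) | 9.00 | 0.587 |
| 29/52 (surgical as MG, no cohort 3) | 10.04 | 0.453 |
| 60% | 10.80 | 0.363 |
| 70% | 12.60 | 0.194 |
| 100% | 18.00 | 0.015 |

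The probability falls below one half once the share exceeds about 54%. At half the planned rate, Reading A fires with probability 0.998 (share 23/62) to 0.983 (share 23/46). It seldom misses slow MG accrual; its weakness is firing when nothing is wrong.

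**Reading B: 9 is the expected MG count and the trigger is half of it, so 4 or fewer.** This needs an MG share of one half, since 18 × 0.5 = 9. The planned sizes give that share in more than one way:

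- Primary cohorts only: 23/46 = 0.5.
- All cohorts enrolling, with the six surgical patients counted as MG and cohort 3 at its lower bound of 6: (23 + 6)/(23 + 23 + 6 + 6) = 29/58 = 0.5.
- The study minimum of 28, which equals 14 + 14, the first stages of the two primary cohorts: 14/28 = 0.5.

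Counting surgical patients as MG is an assumption, but Section 4.1 supports it. Surgical patients must have a high-grade glioma, or a low-grade glioma suspected of progressing, and those whose histology is not high-grade glioma are replaced. On Reading B, P(X ≤ 4 | mean 9) = 0.055 on plan and P(X ≤ 4 | mean 4.5) = 0.532 at half rate.

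**Would a whole-study trigger be better?** The figure would then be 9 or fewer of 18, with P(X ≤ 9 | 18) = 0.015 on plan and P(X ≤ 9 | 9) = 0.587 if all accrual runs at half rate. But the sentence targets MG. Suppose MG is half of accrual and runs at half rate while the other cohorts are on plan. The total mean is 4.5 + 9 = 13.5, and P(X ≤ 9 | 13.5) = 0.135. The whole-study trigger would usually miss the shortfall that the sentence is aimed at.

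**The case for a change.** The strongest case for a change is that no reading works without adding something to the text or removing something from it. Reading A needs 9 to be half of an MG expectation that is nowhere stated. Reading B needs an unstated 50% share. Taking one patient per month as the MG rate alone would make the rule coherent (0.015 on plan), but Sections 3.1 and 11.2 both give the rate for the study. No expected counts are listed for the later checks. The rule is a commitment rather than a prompt for discussion, and clarifying it would take one sentence.

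Most of this stands as a description of the wording. What does not stand is a claim that the figures cannot be reconciled, because 29/58 gives exactly the 9 expected MG patients with every cohort enrolling. A finding of poor specificity is also conditional. It rests on treating cohort sizes as referral proportions, whereas 23 comes from a two-stage test and cohort 3's size from feasibility. The documents give no case mix, and across the shares shown the on-plan firing probability runs from 0.86 down to 0.015. The word arm is loose, but Section 11.2 labels cohort 1 as MG, so the group meant is not seriously in doubt.

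**Conclusion.** The sentence is imprecise about whether 9 is the trigger or the expected MG count, and the study team can settle that when it makes the first check. It does not call for a change to the plan. A trigger that fires early only adds centers. One that fires late delays adding them, and the check repeats every two quarters. Neither touches the 14 + 9 two-stage rule, its error rates, the futility decision or any estimate.

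The obvious rewrite, a whole-study trigger, gives no clear gain. It lowers on-plan firing to 0.015, but it detects half-rate MG accrual with probability only 0.135 when the other cohorts are on plan (Poisson counts, 50% MG share assumed). That is a debatable trade-off, and it abandons the stated MG target. Keeping that target and writing down a share with its counts would tidy the text without altering any result.

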**Stratification Factors: NA**

### **11.3 Analysis of Secondary End Points:**

Data analysis will be conducted for each cohort independently.

1. Progression-free survival: progression-free survival time is defined as the time from a date of treatment start to a date of the initial scan deemed tumor progression while patient is alive or death if there is no more than two missing imaging scans prior to death. The data will be censored if progressive disease was not observed at the time

of data cut-off for analysis. Probability of progression-free survival and median time of progression-free survival will be estimated using Kaplan-Meier method along with 95% confidence intervals.

2. Overall survival: survival time is defined as the time from a date of treatment started to a date of death. The data will be censored if patient was alive at the time of data cut-off for analysis. Overall survival (OS) and median OS will be estimated using Kaplan-Meier method along with 95% confidence interval.
3. Duration of response: duration of response is defined as the time from date of tumor response/per imaging to date of progression. The duration of the response will be summarized using descriptive statistics.
4. Time-to-response: time to response is defined as the time from date of treatment started to date of response per imaging among subjects who have a radiologic response. The duration of the time to response will be summarized using descriptive statistics.
5. Toxicity: NCI Common Terminology Criteria for Adverse Events (CTCAE) version 5.0 will be used for scoring toxicity and adverse events. The severity and frequency of toxicity will be tabulated using descriptive statistics. The proportions of subjects who experienced grade 3 or above toxicities will be estimated, along with 95% confidence intervals by each type of toxicity.

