### **Progressive Disease – PD (defined by *any* of the following):**

- a) **For HGG RANO:**  $\geq 25\%$  increase in sum of the products of perpendicular diameters of enhancing lesions compared to the smallest tumor measurement obtained either at baseline (if no decrease) or best response, on stable or increasing doses of corticosteroids.\*
- b) Any new enhancing or non-enhancing lesion.
- c) Clear clinical deterioration not attributable to other causes apart from the tumor (e.g., seizures, medication adverse effects, complications of therapy, cerebrovascular events, infection, etc.) or changes in corticosteroid dose. The definition of clinical deterioration is left to the discretion of the treating physician, but it is recommended that a decrease in 20% of KPS or from any baseline to 50% or less be considered, unless attributable to comorbid events.
- d) Failure to return for evaluation due to death or deteriorating condition.
- e) Clear progression of non-measurable disease.

\* Stable doses of corticosteroids include patients not on corticosteroids.

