#### **11.4 Analysis of Exploratory Endpoints:**

1. Clinical outcomes such as tumor response rate, progression-free survival, and overall survival for cohort 3 (recurrent BRAF-V600 mutated high-grade primary brain tumors not included in the cohort 1 and cohort 2). The standard definitions of these outcomes will be used as described above. The outcomes will be summarized and presented descriptively.
2. Encorafenib and binimetinib concentrations in enhancing brain tissue and cerebrospinal fluid (surgical cohort): descriptive summary on mean and standard deviation of drug will be reported. Additional analyses are summarized in Section [9.6.1](#).
3. Putative mechanisms of drug resistance are defined as identified genomic or functional alterations in post-treatment tissue that are not present, or are present in a much smaller variant allele frequency (VAF), in pre-treatment tissue, and that could contribute to decreased drug sensitivity. Candidate mutations will be measured using the methods described in Section [9.6.2](#). These results will be manually curated and confirmed against known gene lists.
4. Functional inhibition of the ERK signaling pathway: the functional inhibition of the ERK signaling pathway is defined by the measurements of phospho-ERK and RSK protein, quantitated relative to total ERK. Due to the exploratory nature, the pathway changes after drug exposure will be reported using descriptive summary.

5. BRAF-V600 DNA mutant fraction: the mutant fraction is measured as the number of BRAF V600E or –K transcripts relative to BRAF wild-type transcripts, corrected for differences in sequencing efficiency and the quantity of starting material. The mutant fraction in CSF and plasma will be collected over multiple time points during the study. The fraction change overtime will be presented as a liner or non-linear trend after data checking. Descriptive summary at each individual time point and multiple time points will be presented graphically.

A more detailed description of exploratory correlatives are provided in Section [9.6](#).

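### Duration of response has no censoring rule for responses ongoing at cut-off and no explicit rule for death; secondarily, the PFS event in Section 11.3 does not match the progression definition in Section 8.1

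*Combined protocol and SAP*

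**What the plan says.** **Duration of response.** Section 11.3 item 3 states that "duration of response is defined as the time from date of tumor response/per imaging to date of progression". On analysis it says only: "The duration of the response will be summarized using descriptive statistics". The same section specifies Kaplan-Meier estimation, with a censoring statement, for PFS and for overall survival.

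**PFS.** Section 11.3 item 1 runs PFS from treatment start to the "initial scan deemed tumor progression while patient is alive or death if there is no more than two missing imaging scans" before it. On censoring it says "The data will be censored if progressive disease was not observed at the time" of data cut-off. Section 11.4 carries these definitions to cohort 3: "The standard definitions of these outcomes will be used as described above".

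**Progression elsewhere.** Section 8.1 makes any one of five criteria sufficient for PD. Criterion (c) is "Clear clinical deterioration not attributable to other causes apart from the tumor", and criterion (d) is "Failure to return for evaluation due to death or deteriorating condition". Section 10.1 lists clinical progression as a reason for stopping, separate from progression on MRI, and requires the reason and date of stopping to be recorded.

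**Scan schedule.** MRI is 8-weekly on treatment. Table 9.1 adds one off-treatment MRI, waived if a scan was done in the previous 14 days. It lists none after that, and Section 10.2 then follows survival only.

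**The concern.** Duration of response is a time-to-event quantity. Its longest values are the ones most likely to be unfinished at cut-off. A plain summary must leave those patients out or enter the time observed so far as if the response had ended, and either choice understates duration. Section 11.3 gives the analyst no third route, although it uses one for PFS and overall survival. Nor does it say whether a responder's death without documented progression ends the response.

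For PFS, a patient taken off treatment under 8.1(c), with no scan deemed PD, has progressed under Section 8 but has no event on that date under Section 11. Whether a later death counts depends on whether scans never scheduled after stopping are *missing*, which is not stated. No date is given for censored patients.

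Both are named secondary objectives. Two competent analysts could report different results from the same data, and would be choosing after seeing the data of an open-label trial.

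**Working it through.** The plan gives no figure for either endpoint, so there is none to reproduce.

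**A. Duration of response**

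Inputs from the documents (Section 11.2): 23 patients per primary cohort, 46 in all; one patient per month; target response rate 30%.
- Accrual of the primary patients: 46 / 1 = about 46 months.
- Responders per cohort: 23 × 0.30 = 6.9, about 7.

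Assumptions, not in the documents: exponential duration with true median 9 months (range 6-12), and follow-up after response uniform on 2-48 months (or 2-24 for an earlier cut-off).

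Let λ = ln 2 / 9 = 0.0770, and let G(t) = (48 − t)/46 be the chance that follow-up exceeds t (G = 1 below 2 months).

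1. Share ongoing = (e^(−2λ) − e^(−48λ)) / (46λ) = (0.857 − 0.025) / 3.54 = 0.235.
2. At least one of 7 ongoing: 1 − (1 − 0.235)^7 = 0.85. Mean number: 7 × 0.235 = 1.6.
3. Ongoing treated as complete: solve e^(−λt) G(t) = 0.5. At t = 7.4, 0.566 × 0.883 = 0.50, so the median is 7.4 months.
4. Ongoing dropped: solve ∫₀ᵗ λe^(−λs) G(s) ds = 0.5 × (1 − 0.235) = 0.3825. This gives t = 6.5 months.
5. Kaplan-Meier with ongoing responses censored is aimed at the true 9.0 months.

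| True median | Follow-up | Ongoing | Dropped | Treated as complete |
|---|---|---|---|---|
| 6 | 2-48 | 15% | 4.9 | 5.4 |
| 9 | 2-48 | 23.5% | 6.5 | 7.4 |
| 12 | 2-48 | 31% | 7.7 | 9.1 |
| 9 | 2-24 | 41% | 4.7 | 6.2 |

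Death works the other way. If Kaplan-Meier were used and 10% or 20% of responses ended in a death that was censored rather than counted, the hazard would fall by that fraction. The median would become 9/0.9 = 10.0 or 9/0.8 = 11.25 months.

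**B. PFS**

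Inputs: 8-week scans, and median time to PD 5.5 months. The latter is the midpoint of the 5.3-5.7 month average in Section 2.5 for monotherapy, used here as an exponential median. Assumed: median survival after PD 4 months (range 2-6), and 5% or 10% of patients with clinical progression and no scan deemed PD.

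Kaplan-Meier 6-month PFS by simulation (400,000 patients), 10% share, no stops for other reasons:
- PD by any 8.1 criterion: 49.5%.
- Section 11.3, unscheduled scans not missing, so later deaths count: 52.6% (+3.1 points).
- Section 11.3, unscheduled scans missing, deaths beyond two censored at the last scan: 51.8% (+2.3).

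At a 5% share the shifts are +1.5 and +1.2 points. Over the assumed ranges they are 1.0-1.8 and 0.8-1.3 at 5%, and 2.0-3.7 and 1.7-2.7 at 10%. In cohorts of 23, median PFS shifts on average by 0.2-0.5 months, against a sampling SD of about 1.7 months. The 95% CI half-width for 6-month PFS is 1.96 × √(0.5 × 0.5 / 23) = 0.20, or 20 points.

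With 14% stopping before PD for other reasons and a 10% share, full follow-up gives 49.6%. Section 11.3 gives 54.1% (not missing) or 50.9% (missing). Counting any 8.1 PD and treating unscheduled scans as missing gives 48.6%, which is 1.0 point low.

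**The case against.** **On duration of response.** Section 11.3 does not say that ongoing responses are dropped or treated as complete. With about 7 responders, a descriptive listing could mark them as ongoing. The 9-month median and the follow-up windows are assumptions, and a later cut-off shrinks the effect. This is fair, and it makes the 6.5 and 7.4 months illustrations rather than predictions. It does not supply the missing rule: a median still has to handle those patients somehow.

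A reader might infer that the plan ignores responders' deaths. The documents do not support that. Criterion 8.1(d) makes failure to return because of death PD, so the date of progression arguably already takes in some deaths. The 10.0 and 11.25 month figures also presume Kaplan-Meier, which 11.3 does not name for this endpoint. What stands is that the rule should be explicit.

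**On PFS.** A reader might infer that the scan-based event is an error that materially inflates PFS. That is not supported either.
- The share of clinical-only progressors has no source in the documents.
- The off-treatment MRI, and the repeat imaging recommended in Section 4.4.3 on suspected deterioration, will catch many cases.
- Scan dating is defensible in an open-label trial, because "The definition of clinical deterioration is left to the discretion of the treating physician".
- Changing the event definition while counting unscheduled scans as missing can replace a small upward bias with a similar downward one. At a 5% share with 14% other stops, +0.3 points becomes −0.8.

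Gaps as large as 14.6 points (38.5% against 23.9% at 12 months) appear only with a 30% clinical-only share, 6 months' median survival after PD and censoring at cut-off together. They should not set the severity.

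**Conclusion.** The main point holds. Section 11.3 gives duration of response no censoring for ongoing responses and no explicit rule for death, while using the suitable method for the neighbouring endpoints. Under the stated assumptions the reported median would fall from 9 months to 6.5 or 7.4, and further with an earlier cut-off. The direction follows from dropping ongoing responses or treating them as complete; the size depends on the assumed median and follow-up.

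The PFS point is secondary. The event in 11.3 and the PD definition in 8.1 and 10.1 should be reconciled, and two details stated. The expected effect is about 1 to 3 points at 6 months for assumed shares of 5-10% without other-reason stops, systematic but well inside a half-width of about 20 points.

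Only secondary endpoints, and cohort 3 PFS through Section 11.4, are touched. It would be wrong to read this as a threat to the response endpoint or the two-stage rule, since neither uses PFS or duration of response.

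**What to change.** In Section 11.3:

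1. **Duration of response.** Define it from first confirmed CR or PR to PD or death, saying explicitly how this relates to 8.1(d). Censor ongoing responders at the last evaluable tumour assessment. Report the Kaplan-Meier median with a 95% CI.
2. **PFS event.** Report PFS both ways: scan-dated as now, and by any 8.1 criterion with clinical PD dated by the recorded discontinuation date. The sponsor chooses in advance which is main.
3. **PFS censoring.** State the date (last evaluable tumour assessment) and whether scans not scheduled after stopping count as missing, with the other reading as a sensitivity analysis.

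The cost is wording and a little more analysis. Intervals for duration of response will be wide with about 7 responders per cohort. The discontinuation date is only a proxy for the date of clinical progression, and clinical dates are less precise and more subjective than scan dates; that is the reason to show both. Section 10.1 already requires the reasons and dates, so no new data are needed.

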### **10.1 Off Treatment Criteria**

In the absence of treatment delays due to adverse event(s), treatment may continue until one of the following criteria applies:

- Disease progression on MRI as determined by the local site
- Intercurrent illness that prevents further administration of treatment
- Unacceptable adverse event(s)
- Patient decides to withdraw from the study
- General or specific changes in the patient's condition render the patient unacceptable for further treatment in the judgment of the investigator
- Clinical progression
- Patient non-compliance
- Pregnancy
  - All women of child bearing potential should be instructed to contact the investigator immediately if they suspect they might be pregnant (e.g., missed or late menstrual period) at any time during study participation.
  - The investigator must immediately notify CTEP in the event of a confirmed pregnancy in a patient participating in the study.
- The drug manufacturer can no longer provide the study agent

The reason(s) for protocol therapy discontinuation, the reason(s) for study removal, and the corresponding dates must be documented in the Case Report Form (CRF).

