## **10.2 Off Study Criteria**

Patients will only be off study at the time of death. All patients will be followed for survival every 2 months for the first two years from the off-treatment date; after 2 years, patients will be followed every 6 months until death. Survival status may be obtained by phone call, clinic visit, or medical records (e.g. physician notes/laboratory results of clinic or hospital visit). Please note that additional survival status reports will be required twice yearly for ABTC Central Office reporting.

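### Duration of response has no censoring rule and only a descriptive summary, so responders who have not progressed have no value

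*Combined protocol and SAP*

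**What the plan says.** Evaluating duration of response in patients with a partial or complete response is secondary objective 2 (Section 1.0). Section 11.3 item 3 defines it: "duration of response is defined as the time from date of tumor response/per imaging to date of progression". The whole analysis is then one sentence: "The duration of the response will be summarized using descriptive statistics". No censoring rule, cut-off date or interval is given.

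Items 1 and 2 of the same section are fuller. PFS and OS are each censored when the event has not been seen at data cut-off. For PFS, "median time of progression-free survival will be estimated using Kaplan-Meier method along with 95% confidence intervals"; OS is handled the same way. PFS also has a rule for death, which counts as an event only under a condition: "death if there is no more than two missing imaging scans prior to death".

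Sections 8.1, 8.2, 10.1, 10.2 and 11.4 contain no censoring rule for duration of response. Section 8.1 has its own statement on death; criterion (d) for progressive disease is "Failure to return for evaluation due to death or deteriorating condition".

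**The concern.** A duration that ends only at progression does not exist for a responder who has not progressed. Two groups are affected:

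- **Still in response at data cut-off.**
- **Stopped treatment without progression.** Section 10.1 allows this for several reasons, such as "Intercurrent illness that prevents further administration of treatment", adverse events, withdrawal or non-compliance. Table 9.1 places the last MRI at the off-treatment visit. After that, Section 10.2 specifies survival follow-up: "All patients will be followed for survival every 2 months for the first two years from the off-treatment date". A later progression date may never be recorded.

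Patients with the longest responses are the most likely to lack a progression date. If they are left out, the reported duration is usually too short. If they are included in some way, that way is chosen after the data are seen.

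The death rules add a related problem. Criterion 8.1(d) counts failure to return because of death as progression, with no limit on missed scans. PFS counts a death only when no more than two scans are missing. The same death can therefore be progression in Section 8.1 and not a PFS event in Section 11.3. Because duration of response ends at progression and does not mention death, it inherits this ambiguity.

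**Working it through.** The plan gives no figure for duration of response, so there is none to reproduce. The calculation below shows how far a progressors-only summary could be from the truth.

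**Inputs from the documents**

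- Cohort size 23 and target response rate 30% (Section 11.2): 0.30 × 23 = 6.9, so about 7 responders.
- Accrual of one patient per month (Section 11.2). If shared across the trial, this means 46 months for the two primary cohorts or 62 months for the maximum enrolment in Section 3.1.
- The Slow Accrual Plan sets its trigger at 50% or less "on the MG arm at the end of quarter 6 (9 patients) or every 2 quarters afterwards". If 9 is half of the expected number, 18 patients are expected in 18 months, which is one per month on that cohort alone and 23 months to fill it.
- Scans every 8 weeks (Sections 8.1 and 8.2).

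**Assumptions, not in the documents:** exponential duration with median M; response 2 months after entry; uniform accrual over A months; cut-off F = 6 or 12 months after last entry; no other loss to follow-up.

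**Share still responding at cut-off.** Let λ = ln 2 / M. Follow-up after response is uniform from F − 2 to A + F − 2, so

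share = [exp(−λ(F − 2)) − exp(−λ(A + F − 2))] / (λA).

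For M = 12, λ = 0.05776:

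- A = 23, F = 6: (0.7937 − 0.2102) / 1.3285 = 0.44
- A = 23, F = 12: (0.5612 − 0.1486) / 1.3285 = 0.31
- A = 46, F = 6: (0.7937 − 0.0557) / 2.657 = 0.28
- A = 62, F = 12: (0.5612 − 0.0156) / 3.581 = 0.15

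Of 7 responders, 44% and 31% are about 3 and 2 patients. The chance that at least one of 7 is still responding is 1 − (1 − share)^7, which runs from 0.69 (share 0.15) to 0.98 (share 0.44).

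**Median among progressors only.** With a = F − 2 and b = A + F − 2, the median m (when it lies between a and b) solves

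1 − {[exp(−λa) − exp(−λm)]/λ + (b − m)exp(−λm)} / A = (1 − share)/2.

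For M = 12, A = 23, F = 6 and m = 5.77, the left side is 1 − (1.335 + 15.213)/23 = 0.280 and the right side is 0.561/2 = 0.280.

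| True median (months) | Progressors only, 23 months' accrual | Progressors only, 46–62 months' accrual |
|---|---|---|
| 6 | 4.3–5.1 | 5.1–5.6 |
| 9 | 5.2–6.5 | 6.7–7.8 |
| 12 | 5.8–7.3 | 7.9–9.5 |
| 18 | 6.4–8.3 | 9.6–12.1 |

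For a true median of 12 the true mean is 12 / ln 2 = 17.3 months. The progressors-only mean is about 7.1–8.7 (23 months) or 10.5–12.7 (46–62 months).

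**With the scan schedule.** If progression is seen only at the next 56-day scan, the observable median for a true 12 is 12.9 months. Progressors alone give 7.4 (23 months) or 9.2–11.0 (46–62 months).

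**Direction in small cohorts.** In simulated cohorts of 7 with at least one ongoing responder (true median 12), leaving out the ongoing responders raised the median in 0.2–4.2% and the mean in 0.2–6.0%. The usual direction is downward, but it is not certain.

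**Precision of the alternative.** With 7 responders, a true median of 12 and a log-log Kaplan-Meier interval, the upper 95% limit is not reached in 54–95% of cohorts (58–97% on the scan schedule). This treats the limit as undefined once the curve reaches zero; counting it as reached there gives 20–69%. The typical lower limit on the scan schedule is the first scan after response, 1.8 months.

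**The case against.** The plan never says that ongoing responders are dropped. Section 11.4 item 1 presents cohort 3 PFS and OS descriptively while keeping their earlier definitions, so the word need not exclude censored data. A Kaplan-Meier median or a marked listing could also be called descriptive. It follows that the plan leaves the handling open rather than prescribing a biased one, and the figures above depend on one way of filling the gap. But the cohort 3 endpoints rest on definitions that already include censoring, and item 3 has none. Even a Kaplan-Meier median needs a censoring rule.

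The group that stops without progression is narrower than the list in Section 10.1. Clinical deterioration is progression under 8.1(c), and some failures to return are progression under 8.1(d). This stands. The group's size is not estimated, and the simulation covers cut-off censoring only.

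The 12-month case has no source in the documents. The nearest figure is an average of 5.3–5.7 months to progression on BRAF-inhibitor monotherapy (Section 2.5), which is neither the combination nor a duration of response. At a true median of 6 with 46–62 months' accrual, the error is under one month. The 23-month accrual is an inference from the Slow Accrual Plan. Hence the range of scenarios.

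Limiting deaths after missed scans is a recognised choice for PFS, and the mismatch with 8.1(d) arises only when more than two scans are missing. The two statements still disagree for those deaths.

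Finally, Kaplan-Meier with about 7 responders is imprecise, and censoring patients who stop for toxicity assumes that stopping carries no information about later progression. Both points stand; they are reasons to add a listing.

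**Conclusion.** The concern holds. Under the written definition, a responder without progression has no duration of response, and no other section supplies a rule. In the illustration with a true median of 12 months, 15–44% of responders are in that position at cut-off and progressors alone give a median of 5.8–9.5 months, depending on accrual and follow-up. For a true median of 6 the progressors-only range is 4.3–5.6; for 18 it is 6.4–12.1. These sizes rest on the exponential and cut-off assumptions above and on a progressors-only summary, which the plan permits but does not state. That the rule is missing rests on none of them.

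This should be corrected, but it concerns a secondary endpoint. The primary response rate, the sample size and the two-stage decision rule do not change.

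**What to change.** 1. State one rule for death and missed scans that reconciles criterion 8.1(d) with the PFS definition, and use it for both PFS and duration of response.
2. Define duration of response as the time from first documented CR or PR to progression or death under that rule.
3. Censor patients who are alive and still in response at their last tumour assessment, including those who stopped treatment without progression. Item 1 names no censoring date for PFS, so state the same date there.
4. Replace the descriptive-statistics sentence with the Kaplan-Meier median and 95% CI for each cohort, plus a listing of every responder's duration with ongoing responses marked. Giving the reason for stopping in the listing would show where censoring may be informative.

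The cost is a few sentences in Sections 11.3 and 8.1, with no new data and no change to the sample size or decision rule. The drawback is a wide, often open-ended interval with about 7 responders per cohort, so the listing will carry much of the information.
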